The maximum clinical dose was determined from dog data as the pharmacokinetic is not linear in rats with differences between sexes. Based on these elements and the Guidance for Industry M3(R2) FDA. The maximum clinical dose should not be higher than half of the AUC at the highest dose tested in dogs not showing toxicity (considered as NOAEL).

The mean AUC at the highest dose not showing toxicity in dogs (4.5mg/kg twice daily) is 376.46 ng/ml.h⁻¹ (Table 1). Therefore, half of the AUC is 188.23 ng/ml.h, which corresponds to a dose of 135.79 mg in a human being weighing 60kg.

According to the model, the corresponding AUC for a 60 mg daily dose in humans is 83.15 ng/ml.hr, which is far below 188.23 ng/ml.h (Table 5).

Data on C_{max} are consistent with those on AUC. The half of the C_{max} in dogs receiving 4.5 mg/kg twice daily is 23.77 ng/ml while the C_{max} in humans receiving a total daily dose of 60 mg is 10.57 ng/ml. Thus, the target dose of 60 mg/day (30 mg BID) can be considered as safe in humans.

Table 5: Predicted mean plasma Cmax and AUC(0-inf) in humans following first day dosing of IFB-088 and associated safety coverage

Daily dose (mg)	Daily administered doses (n x mg)	Escalating dose ratio	Expected Human Cmax (ng/ml)	Expected Human AUC (0-inf) (ng/ml.hr)	Cmax safety coverage % of corresponding maximal Cmax in human	AUC safety coverage % of AUC in dog
2.5	1 x 2.5		0.84	3.69	3.5%	0.98%
5	2 x 2.5	2	0.88	6.93	3.7%	1.84%
10	2 x 5	2	1.76	15.32	7.4%	4.07%
20	2 x 10	2	3.52	27.72	14.8%	7.36%
40	2 x 20	2	7.04	55.44	29.6%	14.73%
60	2 x 30	1.5	10.57	83.15	44.47%	22.09%

The escalating dose levels (Table 5) were chosen to not exceed an escalating ratio of 2 except for the last dose level with a smaller ratio of 1.5.

It might be worth noting that the antihypertensive drug Guanabenz, a structural analogue of IFB-088 (with only one atom difference), displays a similar biological activity on PPP1R15A (Tsaytler et al., Science 2011; Das et al., Science 2015) and similar pharmacokinetic profile in Sprague Dawley rats (plasma, brain, retina and sciatic nerve – Report 16-326). Guanabenz is still marketed in certain countries (including Japan) at doses up to 64 mg/day as 32mg/day BID.

Criteria to stop escalating dose:

The dose escalation will be stopped if in a given volunteer:

- The AUC is higher than 111.14 ng/ml.h (simulated AUC for the highest efficient dose in Human and which is lower than the half of AUC in dogs at the NOEL)

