- The C_{max} reaches 23.77 ng/ml.h (half of the C_{max} in dogs at the NOAEL).

The maximum recommended starting dose (MRSD) for IFB-088 in adult healthy volunteers was evaluated at 2.90 mg/day in Humans.

The maximal daily dose to be administered in Humans to cover the different envisioned therapeutic indications was evaluated at 80 mg/day. Therefore, in order ensure optimal safety, **the dose ranges selected are:**

- **2.5 mg/day for the first therapeutic dose;**
- **60 mg/day given as 2 administrations of 30 mg for the highest therapeutic dose.**

1.2.3. *Dose Rationale for the MAD part*

1.2.3.1. *Update on Safety coverage*

Additional toxicology studies have been conducted in rodent (rat) and non-rodent (dog) animal species to further assess IFB-088 safety (see sections 4.3.1 & 4.3.4 of Investigator's Brochure):

- GLP repeated dose toxicity studies in Sprague Dawley rats and Beagle dogs at doses up to 12 mg/kg/day for 13 weeks. Observations and pharmacokinetic parameters of IFB-088 and its major metabolite (IFB-139) are summarized in Table 6.

Table 6: Summary of results from the GLP 13-week toxicology studies in rats and dogs

Study	Regimen	Main findings	analyte	Day of admin.	sexe	Plasma Tmax	Cmax (ng/ml)	AUCt (ng/ml*h)
46232 TSR 13-week toxicology GLP study in Sprague Dawley Rats	Repeated administration 13 weeks P.O.: 1.5 mg/kg BID (6h between the 2 treatments) 3 mg/kg/day	NOAEL	IFB-088	1	Female	T1: 30min	1.69	8.07
					Male	T1: 30min	0.79	5.86
			IFB-088	90	Female	T1: 30min	1.63	8.86
					Male	T1: 10min	0.50	3.79
			Major metabolite IFB-139	1	Female	T1: 3h	1.20	7.85
					Male	T1: 7h	0.98	7.04
	Major metabolite IFB-139	90	Female	T1: 9h	0.93	9.43		
			Male	T1: 7h	1.56	8.98		
	Repeated administration 13 week P.O.: 3 mg/kg BID (6h between the 2 treatments) 6 mg/kg/day	At 6 mg/kg/day administered as 3 mg/kg BID for 13 weeks was considered as adverse due to: - 2 out of 10 males presented enlarged kidneys, with irregular colour and/or surface; these changes correlated with the presence of crystal nephropathy at microscopic examination. - One female presented non-adverse, reversible, minimal bile duct hyperplasia. There were no other remarkable, test item-related signs at 6 mg/kg/day	IFB-088	1	Female	T1: 30min	2.95	26.4
					Male	T1: 30min	2.01	13.4
			IFB-088	90	Female	T1: 30min	2.73	29.9
					Male	T1: 10min	2.94	23.6
			Major metabolite IFB-139	1	Female	T1: 7h	1.20	15.1
					Male	T1: 3h	4.67	36.6
	Major metabolite IFB-139	90	Female	T1: 9h	2.96	36.6		

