Based on results obtained in different CMT animal models, the exposure (AUC_{0-24h}) for optimal efficacy is estimated between 19.89 and 43.18 ng/ml.h and C_{max} for 2 administrations per day in the range of 2.5 to 3.89 ng/ml (Table 7). According to the pharmacokinetics results from the SAD in healthy volunteers, the three following doses of 15, 30 and 50 mg daily cover to the range of optimal efficacy (exposure between 12.82 and 42.62 ng/ml.h, C_{max} between 1.20 and 3.77 ng/ml). The escalating ratio is 2 between the low and middle doses and 1.66 between the middle and high doses. To conclude, the maximal ascending dose will be 50 mg daily (2 x 25 mg) according to the preclinical population pharmacokinetics model and the preliminary pharmacokinetics results of the single day.

Table 8: Predicted mean plasma C_{max} and $AUC(0-inf)$ in humans following 14-day dosing of IFB-088 and associated safety coverage

Daily dose (mg)	Daily administered doses (n x mg)	Escalating dose ratio	Expected Human C_{max} (ng/ml) ⁽¹⁾	Expected Human AUC (0-inf) (ng.hr/ml) ⁽¹⁾	C_{max} safety coverage % of C_{max} in dogs ⁽²⁾	AUC safety coverage % of AUC in dogs ⁽²⁾
15	2 x 7.5	-	1.20	12.82	1.5%	2.5%
30	2 x 15	2	2.26	25.57	2.9%	4.9%
50	2 x 25	1.67	3.77	42.62	4.9%	8.2%
Stopping criteria			23.77	111.14	30.2%	21.5%

(1) Data are extrapolated from pharmacokinetics results of the SAD observed at a daily dose of 60mg (30mg BID), taking into account that IFB-088 C_{max} and AUC are dose-proportional at these dose levels.

(2) Safety coverage is calculated based on C_{max} and AUC_t at NOAEL for the sex with the lowest C_{max} and the lowest AUC_t

Criteria for dose modifications or stopping dose escalation:

The criteria to modify planned doses or stop dose escalation will be the same as the ones used for single ascending dose escalation, as NOAEL in Sprague Dawley rats is maintained and NOAEL in Beagle dogs increased following the results of the 13-week GLP toxicity study, *i.e.*

- $AUC > 111.14$ ng/ml.h, and
- $C_{max} > 23.77$ ng/ml.

Based on the SAD exposure in humans and on the additional toxicity studies performed in animals, the daily doses for the multiple ascending dose to be administered in Humans to cover

the envisioned therapeutic indications (Charcot-Marie-Tooth) and to ensure maximum safety are:

- **15 mg/day given as 2 administrations of 7.5 mg in the first cohort;**
- **30 mg/day given as 2 administrations of 15 mg in the second cohort;**

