3.4. Dose Adjustment/Stopping Criteria

In the SAD part, a starting dose of 2.5 mg of IFB-088 administered as oral capsule was judged to be safe for a first-in-human administration. Escalation to the next higher dose and any dose

adjustments of the next dose levels will be based on safety and tolerability results and available PK data of the previously administered dose group.

In the tentative dosing scheduled, there will be a 2-fold increase from the first dose level (2.5 mg) to the second dose level. The dose levels of the following groups will be increased by 2-fold from the previous dose level, until the dose level of 40 mg, and then 1.5-fold between the 2 last dose levels. The planned dosing schedule may be adjusted to allow administration of intermediate doses.

In the MAD part, the planned doses are 15 mg per day (2 x 7.5 mg at 12-hour interval) in cohort 1, 30 mg per day (2 x 15 mg at 12-hour interval) in cohort 2 and 50 mg per day (2 x 25 mg at 12-hour interval) in cohort 3.

The decision to proceed to the next dose level of IFB-088, will be made by the Dose Escalation Committee based on safety, tolerability and preliminary PK data obtained at the prior dose level.

Dose escalation will stop at doses, which are predicted on the basis of ongoing PK projections, to correspond to concentrations greater than the PK stopping limits (Section 3.4.2).

3.4.1. *Data Package Requirements for Dose Escalation Committee Meetings*

Dataset from a dosing session including IFB-088 plasma concentrations from the previous dose(s)/cohort(s) and safety data including AEs, vital signs, ECG (12-lead) and laboratory parameters up to at least 32 hours post last dose will be available prior to dosing the next group.

The DEC, comprised of the Investigator, the Pharmacologist of the clinical center, the statistician, a representative of the Pharmacovigilance platform, and a Sponsor's representative, will be convened prior to the start of each subsequent dosing session to interpret the clinical safety, tolerability, laboratory data and PK exposure, and make a decision to proceed to the next higher dose. Additional advisors could be invited as required.

A DEC charter will be provided to the members before the start of the study.

The DEC may unblind the treatment assignment for any subject with an SAE or for any treatment group after reasonable justification (e.g. subjects experiencing grade 3 events or findings) (Sibille et al, 2010).

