The DEC will make a recommendation to proceed to the next higher dose as per protocol, or to modify the next dose or to stop the trial.

At the end of each meeting, the DEC will document in writing the decision that has been taken.

3.4.2. *Dose Adjustment/Stopping Pharmacokinetic Criteria*

As pharmacokinetic is not linear in rats with significant differences between males and females, and is linear without sex differences in dogs, dog rather than rat data have been used to modelize human pharmacokinetics.

Dosing will be stopped if the observed AUC(0-inf), at a given dose level in **any** subject, is $> 111.14 \text{ ng/ml.h}^{-1}$ (simulated AUC for the highest efficient dose in Human, lower than the half AUC in dogs at the NOAEL) or if the observed C_{max} is $> 23.77 \text{ ng/ml}$ which corresponds to the half of the C_{max} at the NOAEL in dog.

If the predicted upper limit of 95% CI of AUC(0-inf) at the next dose level is $> 111.14 \text{ ng/ml.h}^{-1}$ or of Cmax is $> 23.77 \text{ ng/ml}$, the next dose level may be decreased, or a decision could be made not to dose further.

3.4.3. *Stopping Safety Criteria*

The dose should not be escalated further if one of the circumstances listed below occurs in subjects within the same cohort, unless it is obvious that the occurrence is not related to the administration of the treatment:

- Occurrence of a Serious Adverse Event considered at least possibly related to the IMP administration in one subject (See Section 8.3). In that case, study has to be immediately interrupted.
- Possibly drug related severe AE in 2 subjects in the same cohort, independent of within or not within the same system-organ-class (EMA Guidelines on strategies to identify and mitigate risks for first-in-human and early clinical trials with investigational medicinal products)
- Clinically significant drug-related laboratory abnormalities of the same character in 2 or more subjects e.g.
 - Alanine aminotransferase (ALT) or aspartate aminotransferase (AST) > 5 times the upper limit of normal (5 ULN) (Grade 3),
 - Creatinine $> 120 \mu\text{mol/L}$ (1.2 ULN) (Grade 1)(FDA's Guidance on Toxicity Grading Scale for Healthy Adult and Adolescent Volunteers Enrolled in Preventive Vaccine Clinical Trials; Sibille et al 2010).

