12. APPENDICES

12.1. Appendix 1: Liver Safety Algorithms

12.2. Appendix 2: Stopping rules

Stopping rules	Individual subject	Within a cohort/dose escalation
ALT or AST $\geq 3 \times$ ULN	1 subject	
ALT or AST $> 5 \times$ ULN		2 subjects
Triglycerides ≥ 5.6 mmol/L	1 subject	2 subjects
Creat $> 1,2 \times$ ULN or Increase in serum creat by $\geq 30 \mu\text{mol/L}$ within 24h or Increase in serum creat to $\geq 1,5 \times$ baseline within 7 days	1 subject	2 subjects
$\beta 2$ microglobuline $\geq 2 \times$ ULN	1 subject	2 subjects
Hematuria $> 2+$ on dipstick verified by cytologic exam, on 2 samples and considered at least possibly related to the IMP	1 subject	2 subjects
QTcB and QTcF > 500 msec or Change from baseline: QTc > 60 msec	1 subject	2 subjects
HR < 45 or HR > 130 bpm*	1 subject	2 subjects
SBP < 80 or SBP > 155 mmHg	1 subject	2 subjects
DBP > 100 mmHg	1 subject	2 subjects
Occurrence of a Serious Adverse Event considered at least possibly related to the IMP administration	1 subject	1 subject
Possibly drug related severe AEs in the same cohort, independent of within or not within the same system-organ		2 subjects
Clinically significant drug-related laboratory abnormalities of the same character		2 subjects
AUC _(0-inf) > 111.14 ng/ml.h ⁻¹ or Cmax > 23.77 ng/ml		1 subject (only for dose escalation)

* When resting heart rate is between 60-100 beats per minutes. Use clinical judgment when characterizing bradycardia among some healthy subject populations, for example, conditioned athletes.

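### The action on an observed PK exceedance is stated inconsistently: Section 3.4.2 stops dosing, while Appendix 2 and the dose rationale stop only escalation; the MAD rationale also joins the two limits with *and* where the other texts have *or*

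*Combined protocol and SAP*

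**What the plan says.** All the documents are parts of the combined protocol and SAP. The rule on an observed exceedance appears in four places.

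- **Section 3.4.2** (operative PK criteria): "Dosing will be stopped if the observed AUC(0-inf), at a given dose level in" any subject is above 111.14 ng/ml.h, *or* if observed Cmax is above 23.77 ng/ml.
- **Appendix 2**, which Section 3.4.3.5 names as the summary of the stopping rules: the same two limits joined by *or*. The individual-subject column is blank, and the cohort/escalation column reads "1 subject (only for dose escalation").
- **Section 1.2.2.3** (SAD rationale): "The dose escalation will be stopped if in a given volunteer" meets one of two bulleted limits. No connective stands between the bullets.
- **Section 1.2.3.2** (MAD rationale): the criteria to modify planned doses or stop escalation "will be the same as the ones used for single ascending dose escalation". The two limits are then listed with *and* between them.

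On timing, Section 6.3.3 puts the plasma and urine assays after completion of each cohort, and Section 9.3.3 puts the statistical analysis after each cohort.

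**The concern.** This is a decision rule in a first-in-human trial, and the same data lead to different actions depending on which page is open. Stopping dosing and not escalating are not loose synonyms in this protocol. The triglyceride rule in Section 3.4.3.2 separates stopping treatment for a subject, stopping it for the whole cohort, and not escalating, and Appendix 2 gives individual and cohort/escalation actions separate columns. The word *only* in Appendix 2 therefore excludes something that Section 3.4.2 appears to require.

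Take one subject with AUC above 111.14 and Cmax below 23.77. Section 3.4.2 stops dosing. Section 1.2.2.3 and Appendix 2 stop escalation. Section 1.2.3.2, read literally, does nothing. The Dose Escalation Committee would have to choose among these after seeing the data.

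**Working it through.** **1. The plan's own figures.** The stopping row of Table 8 expresses the limits as a percentage of dog NOAEL exposure, using the lower sex (Section 1.2.3.1: AUCt 517.0 ng/ml.h, Cmax 78.6 ng/ml). 111.14/517.0 = 21.5% and 23.77/78.6 = 30.2%. Both match Table 8. The limits are consistent; only the logic and the action differ.

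**2. Action, side by side.**

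| Place | Action on an observed exceedance | Connective |
|---|---|---|
| 3.4.2 | Stop dosing | or |
| Appendix 2 | Stop escalation only | or |
| 1.2.2.3 (SAD) | Stop escalation | none given |
| 1.2.3.2 (MAD) | Modify doses or stop escalation | and |

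With concentrations available only after the cohort (6.3.3, 9.3.3), a stop of dosing cannot reach the cohort that produced the exceedance. What remains is the next step. A rule that stops dosing leaves no further dosing; a rule that stops only escalation leaves open more dosing at the same or a lower level. The texts give different answers.

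**3. Connective.** Expected exposure at 50 mg/day (Table 8): AUC 42.62, Cmax 3.77.
- AUC limit: 111.14/42.62 = 2.6 times expected.
- Cmax limit: 23.77/3.77 = 6.3 times expected.

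If both measures rise in proportion, then between these multiples *or* triggers and a literal *and* does not.

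**4. How likely is a trigger?** Inputs: AUC0-24h of 51.41 +/- 20.45 in the SAD (Section 1.2.3.2), taken as mean and SD at 60 mg/day. Scaling Table 8 gives 42.62 × 60/50 = 51.1, which agrees. Six active subjects per cohort.
- CV = 20.45/51.41 = 0.398; lognormal sigma = sqrt(ln(1 + 0.398²)) = 0.383.
- Chance that any of six exceeds = 1 − (1 − q)^6, where q is one subject's chance of AUC above 111.14.

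| Dose, mean AUC | Normal: q; any of 6 | Lognormal: q; any of 6 |
|---|---|---|
| 30 mg/day, 25.57 | about 0; about 0 | any of 6: 0.02% |
| 50 mg/day, 42.62 | 0.0000265; 0.02% | 0.00355; 2.1% |
| 60 mg/day, 51.41 | 0.0017; 1.0% | 0.0138; 8.0% |

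For 60 mg/day, normal: z = (111.14 − 51.41)/20.45 = 2.92. Lognormal: z = (ln 111.14 − ln 51.41 + 0.383²/2)/0.383 = 2.20. The 60 mg/day row is included because Section 3.1.2 sets that as the MAD predefined maximum, although the planned top cohort is 50 mg/day.

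A literal *and* also needs Cmax above 23.77. The documents give no Cmax CV. Assuming 30% to 60% and a lognormal spread, the chance for any of six at 50 mg/day is at most about 0.1%, so a literal *and* would almost never trigger.

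**The case against.** **The connective is nearly settled by the text.** Section 1.2.3.2 says the MAD criteria are those of the SAD, and the operative Section 3.4.2 and Appendix 2 both say *or*. In a bulleted list of criteria, *and* naturally joins items. This largely stands, and so the connective is secondary. It is not fully closed, because the SAD list has no connective to refer back to, and the QTc criterion in Section 3.4.3.4 uses *and* and *or* as logical operators.

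**The action makes little difference.** With assay after the cohort, neither wording can halt that cohort. SAD results are already reported, so the rule now acts only in the MAD. The 50 mg/day cohort is the last planned, and at 30 mg/day, where a planned escalation follows, a trigger has a chance of at most 0.02% at expected exposure. This is fair and limits the severity. It does not remove the conflict: a stopping rule is there for exposure that departs from expectation, and the texts still differ on dosing at the same or a lower level.

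**A reader might also infer that the two predictive rules conflict.** Section 3.4 says "Dose escalation will stop at doses, which are predicted on the basis of ongoing PK projections" to exceed the limits. Section 3.4.2 adds "If the predicted upper limit of 95% CI of AUC(0-inf) at the next dose level is" above the limit, then "the next dose level may be decreased, or a decision could be made not to dose further". The documents do not support a contradiction. A permission does not contradict a requirement: stopping satisfies both, and the upper-limit trigger can be read as an earlier caution below a ceiling. Section 3.4 does not say that its prediction is a point estimate. Whether the interval is for a mean or an individual is missing detail, not a conflict, and Section 9.3.3 leaves the content of the committee's statistical report to a charter that is not among the documents.

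**Conclusion.** The inconsistency is real and concerns an observed exceedance. The main fault is the action: stop dosing in Section 3.4.2 against escalation only in Appendix 2, with the rationale sections also referring to escalation. The secondary fault is *and* in Section 1.2.3.2 against *or* elsewhere.

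Severity is minor to should-fix. At expected exposure a trigger is improbable at 50 mg/day and uncommon at 60 mg/day, so the conflict bites only if exposure is unexpectedly high. The probabilities rest on a 40% CV from the SAD, dose proportionality, independent subjects, AUC0-24h standing in for AUC(0-inf), and single-day exposure standing in for MAD exposure. The contradiction in wording needs none of these.

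A reader might go further and conclude that the MAD has no working AUC limit, or that the AUC to be compared is undefined. Neither follows: Sections 3.4.2 and 3.4 cover both parts, and Section 3.4.2 and Appendix 2 both name AUC(0-inf).

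**What to change.** Reconcile Sections 1.2.2.3, 1.2.3.2 and 3.4.2 and Appendix 2 into one statement, with one connective and one action on an observed exceedance. The action should be one that can be carried out at the time concentrations become available under Sections 6.3.3 and 9.3.3, and the statement should say whether further dosing at the same or a lower level is allowed. Which version is right is for the sponsor to decide.

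Editorial only: Section 1.2.2.3 has Cmax "reaches 23.77 ng/ml.h", where the other places use a strict inequality and ng/ml. The value 83.15 is labelled AUC(0-inf) in Table 5 but AUC0-24 in Section 1.2.3.2.

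The cost is wording in four places, possibly through a protocol amendment under Section 10.1.3. No samples, visits or subjects are added.

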Moreover, the occurrence of moderate adverse reactions within the same system-organ-class in more than one subject, and/or clinically significant changes from baseline measurements will be considered as a safety signal and will have to lead to increase caution and a closer assessment of safety parameters in the other subjects. In such a case, data from all subjects would be to be reviewed.

3.4.3.1. *Liver Chemistry Stopping Criteria*

Liver chemistry threshold stopping criteria have been designed to ensure subject safety and to evaluate liver event etiology (in alignment with the FDA premarketing clinical liver safety guidance).

Study treatment will be stopped **for a subject** if the following liver chemistry stopping criteria is met:

- ALT or AST $\geq 3\text{xULN}$

Refer to Section 8.10, Liver Chemistry Follow-up Procedures, for details of the required assessments if a subject meets the above criteria.

3.4.3.2. *Triglycerides Stopping Criteria*

Several subjects experienced hypertriglyceridemia during the SAD part of the study. All cases were below the threshold of 5.6 mmol/L (i.e. 5 g/L), above which hypertriglyceridemia is considered clinically significant (European Atherosclerosis Society, European Society of Cardiology, French Society of Endocrinology) and no correlation or possible dose relationship was established. Moreover, some subjects with hypertriglyceridemia were in the placebo groups.

Nevertheless, a stopping criterion for triglycerides has been added in the MAD part of the study:

Study treatment will be stopped for a subject if the following criterion is met:

- Serum triglycerides ≥ 5.6 mmol/L and the subject is receiving IFB-088

Study treatment will be stopped for the whole cohort and the dose will not be escalated, if the following criterion is met:

- Serum triglycerides ≥ 5.6 mmol/L in 2 subjects receiving IFB-088.

Next cohort could be administered a lower dose intermediate between the previous cohort and the present cohort.

3.4.3.3. *Renal disorders*

The dose should not be escalated further if one of the circumstances listed below occurs **in 2 or more subjects** within the same cohort:

- Creatinine > 120 $\mu\text{mol/L}$ (1.2 ULN) (Grade 1)
- Or a change from baseline ≥ 30 $\mu\text{mol/L}$ within 24 h
- Or a change from baseline $\geq 50\%$ within one week

(KDIGO definition Ostermann and Joannidis, 2016)

- Hematuria $> 2+$, verified by cytologic exam, on 2 samples and considered at least possibly related to the IMP

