- Urinary ratio Beta 2 microglobulin/ creatinine $\geq 2\text{N}$

One subject that will meet one of these criteria above will be withdrawn from the study.

3.4.3.4. *QTc Withdrawal Criteria*

A subject that meets the criteria below will be withdrawn from the study. The QT correction formula used to determine discontinuation should be the same throughout the study.

- QTcB and QTcF > 500 msec, OR
- Change from baseline: QTc > 60 msec

Withdrawal decisions are to be based on an average QTc value of triplicate ECGs. If an ECG demonstrates a prolonged QT interval, obtain 2 more ECGs over a brief period, and then use the averaged QTc values of the 3 ECGs to determine whether the subject should be discontinued from the study.

The dose should not be escalated further if 2 or more subjects present a prolonged QT interval as defined above.

3.4.3.5. *Vital Sign Withdrawal Criteria*

The dose should not be escalated further if 2 or more subjects, within a dose-level, receiving IFB-088 experience a grade 3 vital signs (heart rate and/or blood pressure) adverse event that are deemed possible or probably related to study drug by the investigator.

The grading for adverse events is based on FDA's Guidance on Toxicity Grading Scale for Healthy Adult and Adolescent Volunteers Enrolled in Preventive Vaccine Clinical Trials:

Vital Signs*	Grade 3
Tachycardia (beats per minute)	> 130
Bradycardia - beats per minute**	< 45
Hypertension (systolic) - mm Hg	> 155
Hypertension (diastolic) – mm Hg	> 100
Hypotension (systolic) – mm Hg	< 80

*Assuming supine position, at least 5 min at rest conditions, not sleeping subjects, measurements on the same arm and several concordant results

**When resting heart rate is between 60-100 beats per minutes. Use clinical judgment when characterizing bradycardia among some healthy subject populations, for example, conditioned athletes.

Stopping rules for an individual subject, for the dose escalation and within a cohort are summarized in [Appendix 2](#).

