- **Definitely:** a reaction that follows a reasonable temporal sequence from administration of the drug, or in which the drug level has been established in body fluids or tissues, that follows a known or expected response pattern to the suspected drug, and that is confirmed by improvement on stopping or reducing the dosage of the drug, and reappearance of the reaction on repeated exposure (re-challenge if applicable).

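### The relatedness condition for stopping dose escalation is not the same in sections 3.4.3, 3.4.3.3, 3.4.3.5 and Appendix 2

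*Combined protocol and SAP*

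**What the plan says.** Section 3.4.3 opens with "The dose should not be escalated further if one of the circumstances listed below occurs" among subjects of one cohort, and adds an exit: "unless it is obvious that the occurrence is not related to the administration of the treatment". Three rules follow, each with its own relatedness term:

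- serious events: "Occurrence of a Serious Adverse Event considered at least possibly related to the IMP administration in one subject";
- severe events: "Possibly drug related severe AE in 2 subjects in the same cohort";
- laboratory values: "Clinically significant drug-related laboratory abnormalities of the same character in 2 or more subjects e.g", with ALT or AST above 5 ULN and creatinine above 120 µmol/L (given as 1.2 ULN) as the two examples.

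Section 3.4.3.3 has its own lead-in, without the exit: "The dose should not be escalated further if one of the circumstances listed below occurs in 2 or more subjects within the same cohort". Creatinine above 120 µmol/L is first on its list, with no relatedness or significance wording. Hematuria, on the same list, must be judged at least possibly related.

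Section 3.4.3.5 counts grade 3 heart-rate and blood-pressure events in subjects on IFB-088, and only those "that are deemed possible or probably related to study drug by the investigator". It closes by naming Appendix 2 as the summary of the stopping rules.

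Appendix 2 sets the escalation count at 2 subjects in separate rows for creatinine, ALT/AST above 5 ULN, heart rate, systolic pressure and diastolic pressure. None of these rows carries a relatedness or active-treatment condition. A further row covers drug-related laboratory abnormalities in general.

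Section 8.6.2 has five causality levels: *Not related*, *Unlikely*, *Possibly*, *Probably* and *Definitely*.

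**The concern.** In a first-in-human study the escalation rule is the main decision rule, and the Dose Escalation Committee must record each decision in writing (section 3.4.1). If the same two events meet the rule in one place and not in another, the decision depends on which page the committee uses. Section 3 allows no waivers except for immediate safety concerns, so the difference should not be left to be settled informally at a meeting.

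The kidney is where this matters most. Renal findings contributed to setting the rat NOAEL, and drug-induced renal crystals have their own risk section (1.3.2). The active-treatment condition matters as well: applying section 3.4.3.5 requires knowing who is on IFB-088, while applying Appendix 2 does not.

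**Working it through.** The plan attaches no probability to these rules. Its only one, in section 9.2, is a 26% chance of at least one adverse event among 6 actively treated subjects at a true rate of 5%. It reproduces (1 − 0.95^6 = 0.265) but has no bearing here. The check is therefore a comparison of texts.

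**Step 1. Conditions side by side, for 2 subjects in a cohort**

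| Event | Body section | Condition in the body | Condition in its Appendix 2 row |
|---|---|---|---|
| Creatinine > 120 µmol/L | 3.4.3 | clinical significance, drug-related, exit for plainly unrelated | none |
| Creatinine > 120 µmol/L | 3.4.3.3 | none stated; reach of the exit unclear | none |
| ALT or AST > 5 ULN | 3.4.3 | clinical significance, drug-related, exit | none |
| Grade 3 heart rate or blood pressure | 3.4.3.5 | on IFB-088; possible or probable | none |
| Hematuria > 2+ | 3.4.3.3 | at least possibly related | at least possibly related |

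The hematuria row is informative. Both 3.4.3.3 and Appendix 2 state a relatedness condition there, so its absence from the other rows cannot simply be read as abbreviation.

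**Step 2. Apply each text to the same two events.** Assumption: drug-related, which is not a level in 8.6.2, means *Possibly* or higher.

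1. Creatinine > 120 µmol/L, both rated *Unlikely*. The 3.4.3 laboratory rule is not met; 3.4.3.3 is met; the Appendix 2 creatinine row is met. The 3.4.3 exit alone would not excuse these events, since it covers only the plainly unrelated. The word drug-related in the rule itself excludes them.
2. Creatinine > 120 µmol/L, both plainly unrelated. The 3.4.3 rule is not met. Section 3.4.3.3 is met if the exit stays in 3.4.3, and excused if the exit reaches the sub-sections. The Appendix 2 row is met.
3. ALT > 5 ULN, both *Unlikely*. The 3.4.3 rule is not met, and 3.4.3.1 governs only the individual subject's treatment. The Appendix 2 row is met.
4. Heart rate > 130 bpm in two IFB-088 subjects, both *Unlikely*. Section 3.4.3.5 is not met, nor is the severe-event rule in 3.4.3. The Appendix 2 row is met.
5. Heart rate > 130 bpm in one IFB-088 and one placebo subject. Section 3.4.3.5 is not met, whatever the rating; the Appendix 2 row is met. The severe-event rule, which does not mention arm, might also apply, so case 4 is the cleaner example. Triglycerides show the same difference over active treatment between 3.4.3.2 and Appendix 2.

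**Step 3. Map the terms onto 8.6.2 (lesser point)**

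- The serious-event rule maps cleanly to *Possibly*, *Probably* and *Definitely*.
- The severe-event rule, taken literally, names *Possibly* alone.
- The laboratory term is not a level.
- The vital-sign rule names two levels and leaves out *Definitely*, which 8.6.2 begins to define as "a reaction that follows a reasonable temporal sequence from administration of the drug".

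**The case against.** The strongest reply is that the rules are alternatives: any one that is met stops escalation. An unmet rule in 3.4.3 is then silent; it does not tell anyone to escalate. For creatinine, 3.4.3.3 is the specific renal rule, the Appendix 2 creatinine row agrees with it, and 3.4.3 mentions creatinine only as an example. This has force. A reader might infer that the two creatinine texts command contrary actions, and the documents do not support that. What stays open is case 2: whether the exit in the parent section reaches its sub-sections.

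The reply does not settle vital signs or ALT/AST. There the disagreement is between a rule and its summary. If any row of Appendix 2 is enough on its own, the conditions written into 3.4.3.5, and those on ALT/AST in 3.4.3, have no effect on escalation at these thresholds. The plan does not say that this is intended.

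A reader might also infer that events rated *Definitely* escape the vital-sign rule. The omission is probably loose wording for a minimum level, and the Appendix 2 rows would catch such events anyway. Nor do the documents show that twice-daily dosing over 14 days would bring vital-sign effects to *Definitely* through recurrence. From Day 3, scheduled vital signs are taken in the morning before dosing. Section 8.6.2 also asks for a known or expected response pattern and improvement on stopping or reducing the drug. Appendix 2 stops an individual after a single vital-sign crossing.

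Finally, causality need not be judged blind at the decision: sections 3.4.1 and 5.1 let the committee unblind, with grade 3 events named as a reason. The committee's charter may clarify some of this, but it is not among the documents.

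**Conclusion.** The inconsistency stands. It is an error in the text as written, not a missing detail. Five Appendix 2 rows are affected: creatinine, ALT/AST above 5 ULN, heart rate, systolic and diastolic pressure.

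For ALT/AST and vital signs, two events rated *Unlikely* stop escalation under Appendix 2 and do not under the section it summarises. The ALT/AST part rests on reading drug-related as *Possibly* or higher; the vital-sign part needs no such assumption. For creatinine, the open matter is whether the relatedness and significance wording and the exit in 3.4.3 have any effect, given 3.4.3.3. The mismatch with the 8.6.2 levels is secondary.

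No frequency can be given. The documents contain neither the chance of crossing these thresholds nor the share of crossings that would be judged unrelated. A probability built on assumed crossing rates would show how often two subjects cross, not how often the texts disagree.

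**What to change.** Reconcile sections 3.4.3 to 3.4.3.5 with Appendix 2, so that each rule states once:

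- which 8.6.2 levels count, or that no relatedness condition applies;
- whether a clinical-significance condition applies to creatinine and ALT/AST;
- whether only subjects on IFB-088 count;
- whether the 3.4.3 exit applies to 3.4.3.1 through 3.4.3.5.

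Appendix 2 should carry the same conditions as the sections it summarises. This review does not say which version of any rule is right; that is for the sponsor and investigators.

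The cost is wording in a protocol amendment and in the committee's charter. It needs no extra subjects, visits or assays.
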